	Pre-intervention	Post-intervention	Follow-up interview/recording (intervention arm only)
Demographics	X		
Provider burnout	X	X	
Provider/patient engagement in shared decision-making, measured qualitatively	X		X

B. Sample Size:

Specific Aim 1: We based our sample size calculation on our primary outcome, contraceptive continuation. Based on our previous studies in this population, we estimate that 50% of women in our control group will continue with their contraceptive method at seven months. Using this same data, we have calculated the intra-cluster correlation (ICC) of this response by provider and by clinic at ~0 and 0.021 respectively. Accounting for clustering and 20% loss to follow-up, as well as a inflation factor to account for differences in contraceptive initiation among those in clinics with IUDs and implants on-site as compared to those without these methods on site, a sample of 758 patients (approximately 32 patients for each of 24 providers) would provide 80% power in 2-sided tests with a type-I error rate of 5% to detect a 12 percentage point increase in continuation, to 62%. This difference in contraceptive continuation would be clinically meaningful and is consistent with effects reported in the contraceptive literature. Again using data from our previous study to estimate ICCs and baseline parameters, the sample will also provide 80% power to detect small-to-moderate but clinically significant differences in secondary outcomes as shown below.

Study Protocol

Patient Centered Support for Contraceptive Decision-Making: A Cluster Randomized Controlled Trial of a Contraceptive Decision-Support Tool

November 22, 2016

Outcome	ICC		Design effect	Baseline SD/%	SES/ MDD
	Clinic	Provider			
Continuous measures					
Decision conflict scale	0.000	0.027	1.3	1.9	0.25
Satisfaction score	0.152	0.075	1.7	6.5	0.31
Dichotomous measures					
Choice of highly effective method	0.096	0.000	0.9	23%	10.9%
Shared decision making	0.006	0.024	1.3	46%	14.3%
Unintended pregnancy	0.005	0.001	1.0	5%	-4.5%
For continuous outcomes, the standard deviation (SD) and standardized effect size (SES) are reported; for binary outcomes, the baseline prevalence and absolute effect, both in percent.					

Specific Aim 2: We have estimated that audio recording 2-3 patient encounters at each time point (before and after implementation of the intervention) for each of the providers randomized to the intervention will allow us to achieve saturation and to meaningfully compare the pre- and post-intervention period.

Specific Aim 3: We will conduct focus groups at each of the four clinics involved in the study, and will conduct semi-structured interviews of each of the providers randomized to the intervention. For our quantitative measures, we estimate we will have the ability to detect a less than 0.5 SD difference in consultation time and total clinic visit time. For comparison of burnout among providers, our sample size will be 24, with 12 in each group, and therefore will have limited power. In order to optimize power, we will estimate treatment effects on the final score controlling for the baseline value. Using this measure, we anticipate having 80% power to detect a 0.5 to 1.1SD differences on each of the sub-scales of the Maslach Burnout Inventory, depending on with within-provider correlation of these responses.

C. Methods of Analysis

Patient and provider stakeholders will be involved in an iterative manner in all stages of planning of analyses and in data interpretation.

[IR-1] Data required for primary analyses will be inspected, cleaned, and locked before primary analysis is begun. Data checks will include examination of descriptive statistics for plausibility (e.g. plausible

Study Protocol

Patient Centered Support for Contraceptive Decision-Making: A Cluster Randomized Controlled Trial of a Contraceptive Decision-Support Tool

November 22, 2016

participant age, scale values fall within scale options given), distribution, and missingness. Values with errors will be replaced as missing or, if a correction is verifiable through review of an individual's record, replaced with the correct value in the dataset in Stata 14. For the primary analyses, individual record reviews will be performed for any participants with circumstances in which the primary outcome of contraceptive continuation may be complicated. These include all participants who selected DMPA (The Shot or "Depo") as their main or bridge method choice; participants who stopped their method before their 4-month survey and restarted it again before their 7-month survey; participants who transitioned from use of their bridge method to use of their main method for birth control during the course of the study; participants who became pregnant during the course of the study, after their day of enrollment; participants who were not reached to complete a 4-month survey, but did complete a 7-month survey; and participants with partially complete survey records at 4 or 7 months [IR-4]. Participants who are negative for the primary outcome (i.e. discontinuous) at the time of their 4-month survey will be considered negative for the primary outcome at 7 months, regardless of whether they completed a 7-month survey or not. Baseline outcomes will also be examined for individuals who accidentally completed multiple surveys at baseline, with priority given to the first survey completed. Reliability of scales will be assessed using Cronbach's alpha, as well checks for predictive and discriminant validity. [IR-4]. Reliability of scales will be assessed using Cronbach's alpha, as well checks for predictive and discriminant validity.

Specific Aim 1:

We will assess imbalance by treatment assignment using cross-tabulations and comparisons of within group means and medians. Inference for balance on provider covariates will use chi-squared, Fisher's exact, t, and Wilcoxon tests as appropriate, while differences in patient characteristics will be assessed using mixed effects models with fixed effects for clinic and random effects for provider. [IR-3] Primary analyses of treatment effects will be intention-to-treat, according to treatment assignment, and without regard to use of the tool or seeing an intervention provider. Treatment effects will be estimated using mixed effects linear, logistic, proportional odds, and multinomial models, with fixed effects for clinic and random effects for provider.

Missing data. [MD-1] Missing data will have been minimized by active follow-up of participants. [MD-4] Missing data rates for primary and secondary outcomes as well as important covariates will be reported, in combination with summaries of the reasons for missingness, including dropout and pregnancy. [MD-2] All analyses will handle missing data using 20-fold multiple imputation of missing outcomes, based on iterative chained equations. [MD-3] Summary effect estimates, averaged over the 20 imputed datasets, as well as confidence intervals and p-values, will be calculated using standard methods that account for imputation error.

Sensitivity analyses. [MD-5] Because informative missingness would violate the covariate-dependent missing at random (CDMAR) assumption of the standard multiple imputation procedure, we will conduct

Study Protocol

Patient Centered Support for Contraceptive Decision-Making: A Cluster Randomized Controlled Trial of a Contraceptive Decision-Support Tool

November 22, 2016

sensitivity analyses in which we multiply impute missing data under plausible informative missing data mechanisms – in particular, lower contraceptive continuation rates among participants with missing values of this outcome, in one or both arms. [DR-3] In addition, we will conduct sensitivity analyses controlling for any imbalanced pre-randomization characteristics (e.g., age and parity) that predict outcomes, using 5% changes in the coefficient for the intervention as the criterion for covariate inclusion in the adjusted model. To characterize the influence of individual providers, we will estimate best linear unbiased predictions of the provider effects, and also fit models with additional random provider-intervention interactions, to capture heterogeneity in the effects of the intervention. In all analyses, we will transform continuous outcomes as necessary to meet the normality assumption, model departures from linearity in the influence of continuous covariates, check for influential points, and identify potentially important interactions.

Heterogeneity of treatment effects. [HT-1] We will assess modification of the effect of assignment to the intervention by the following 5 pre-specified factors: age, race/ethnicity, language, parental education, and clinic. We will assess evidence for effect modification by adding the effect modifier and its interaction with the treatment assignment indicator to the primary analysis models specified above. To limit inflation of the type-I error rate, we will only estimate within-stratum treatment effects if the interaction is statistically significant at a Bonferroni-corrected $P = 0.01$, and will cautiously interpret findings. These analyses will use multiply imputed data and corresponding inference methods.

Specific Aim 2: For this aim, we will be assessing the effect of the intervention on counseling at the cluster (i.e., provider) level. We will use Dedoose software to analyze the audio recordings using modified grounded theory, with the coding performed by [name], [name], and [name], with input from patient stakeholder representatives. This coding will focus on the presence or absence of shared decision making and patient engagement in the decision making process. In conducting this coding, we will use concepts drawn from observational measures of shared decision making, including the OPTION scale and the Four Habits Coding Scheme, as well as insight into the counseling process gained through our previous observational study, to identify our initial thematic structure. We will perform iterative coding, with discussions between coders, the PI, and patient stakeholders to clarify concepts and resolve ambiguities. We will then, again in collaboration with stakeholders, qualitatively explore the extent to which the providers altered their behaviors following implementation of the intervention using memo writing, and ultimately compiling these into results.

Specific Aim 3: In order to determine the effect of the intervention on the experience of providing family planning care at the level of both the clinic and the provider, we will perform both qualitative and quantitative analyses. Quantitative analyses, including comparing consultation time and total clinic visit time for patients in the intervention and control group, will use similar methods to those described in Aim 1. We will also compare scores on each sub-scale of the Maslach Burnout Inventory (emotional exhaustion, depersonalization, and personal accomplishment), controlling for baseline values, between providers randomized to the intervention and those randomized to the control group in both bivariate

Study Protocol

Patient Centered Support for Contraceptive Decision-Making: A Cluster Randomized Controlled Trial of a Contraceptive Decision-Support Tool

November 22, 2016

and multivariate analyses, again controlling for clustering by clinic. In addition, we will conduct a sensitivity analysis controlling for any imbalanced pre-randomization characteristics (e.g., age) that predict outcomes, using changes in the coefficient for the intervention as the criterion for covariate inclusion in the adjusted model. Thematic analysis of interview and focus group transcripts and recordings will again be performed using Dedoose software, using an iterative and collaborative process of coding as described in Aim 2.

Intention-to-treat analysis

Participants who “cross over” from their assigned study arm (as determined by the provider they are likely to see) will be included in the final analyses in the arm in which they were initially assigned.

Modified intention-to-treat analysis: Post-randomization exclusion

Some participants may be excluded from analysis after being randomized:

- Participants who find out they are pregnant during their enrollment visit (and thus would have been ineligible had this been known prior to enrollment).
- Participants who enrolled in the study more than once (their second enrollment will be excluded).

Additional Analyses

Intervention arm patient participants’ decision support tool data will be analyzed. Participant data input to the tool includes patient preferences around birth control characteristics, their recommended methods, and any questions for their provider.

D. Data Management

Only Key Study Personnel as approved on the UCSF CHR application will have access to study data. As much data as possible will be collected and stored electronically in order to minimize the number of pieces of paper containing PHI and the possibility for participant data to be lost or breached. Collecting data electronically also eliminates the possibility for study staff to make errors in data entry when transferring data from paper to electronic storage.

Surveys

All patient and provider surveys will be administered via REDCap using secure iPads. Survey data will then live in the secure UCSF REDCap database. All user actions in REDCap are tracked by user and time (for example, editing or downloading data). Participant names and contact information will be marked as PHI and will not be downloadable. Only de-identified data will be able to be downloaded by study

Study Protocol

Patient Centered Support for Contraceptive Decision-Making: A Cluster Randomized Controlled Trial of a Contraceptive Decision-Support Tool

November 22, 2016

staff. If downloaded to Excel or Stata for analysis, study datasets will remain on a secure UCSF server accessible only by study staff. Patient follow-up will also be tracked in REDCap.

Note: Surveys for participants who chose vasectomy as their contraceptive method at baseline and started that method will be administered over the phone using paper-based templates rather than REDCap, due to the difficulty associated with programming a survey for this specific method. Upon completion, the survey data will be manually entered into REDCap within one month and the paper-based survey will be shredded.

Consent forms

Paper consent forms and HIPAA authorizations will be stored in locked file cabinets in a locked ward for three years after study completion, according to UCSF IRB stipulations. They will not be linked to participant study IDs.

Time study

Time study data will contain no PHI other than the participant study ID. It will be tracked in an Excel spreadsheet on a secure server.

Audiorecordings and interviews

All audio recordings of patient visits and provider and staff interviews will be managed in accordance with [name] standard operating procedures. This includes promptly transferring recordings off of the recording device and onto a secure UCSF server, having visits transcribed and de-identified in a HIPAA-compliant manner, and storing de-identified transcripts used in qualitative analysis on a secure UCSF server.

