- Each provider will conduct up to 45 family planning visits (not including visits during which the patient participant was given a pregnancy diagnosis, which is a post-randomization exclusion criterion) in the clinic with patients participating in this phase of the study.
- Providers who complete 40 visits before the end of the study will be approached and further recruitment for them is feasible, we will approach them to be re-consented to complete a maximum total of 45 visits per provider, in accordance with our IRB approval.
- After completing study visits for the intervention phase, all providers will complete another short survey via REDCap, consisting of the Maslach Burnout Inventory.

Study Protocol

Patient Centered Support for Contraceptive Decision-Making: A Cluster Randomized Controlled Trial of a Contraceptive Decision-Support Tool

November 22, 2016

- After completing all visits and the second survey, providers in the control arm have completed their participation in the study while providers in the intervention arm move to the post-intervention phase.

In the intervention phase, we will recruit patients at the study clinics. The procedure for patient participants is as follows:

- After being screened and consented by study staff, each patient will complete a pre-visit survey regarding their contraceptive knowledge and preferences and provide her preferred and back-up contact information to the study staff and preferred method of contact for follow-up surveys.

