- **Randomization will be considered the point of enrollment in the study.** For patient participants that are at a clinic that makes appointments with specific providers, this will be decided by the clinic schedule and arm assignment will be recorded upon completion of the pre-visit survey. For patient participants that are at City Clinic and Planned Parenthood, the point of enrollment in the study will be when the randomization procedure described in the previous paragraph has been completed. Prior to being randomized, if an eligible patient participant does not wish to continue with study procedures, they will be considered as a "decline to participate." If they do not wish to continue with study procedures after the point of randomization, they will be considered "dis-enrolled."

Study Protocol

Patient Centered Support for Contraceptive Decision-Making: A Cluster Randomized Controlled Trial of a Contraceptive Decision-Support Tool

November 22, 2016

- If the patient's family planning appointment/randomization assignment is with a provider in the intervention arm, she will interact with the MyBirthControl contraceptive decision support tool while in the waiting room. The RA or volunteer will note the unique tool ID number that is generated on the start screen of the tool and log this in the recruitment tracking log so that back end tool data can be analyzed at a later date.
- In the intervention arm, the tool will generate a printout for each patient that contains information about their preferences for contraception, their reproductive intentions, their medical history, and questions that they have for their provider. This paper will then be shared with the provider. The printout will be destroyed by study staff immediately after the clinic encounter or taken home if the patient requests it, so that it does not become a part of the patient's medical record (in order to limit the possibility of contamination between arms).
- Patients seeing a provider randomized to the control arm will then have a family planning visit in the usual fashion, as performed by that provider.

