- Use of a Highly Effective Method of Contraception at 4 and 7 Months Follow-up
 - Whether patient is using a highly effective contraceptive method at 7 month follow-up survey.
- Continuation of the chosen method 4 months after her visit.
 - Continuation of the chosen method four months after enrollment, without a gap of four consecutive weeks or more.

Specific Aim 2: Qualitative assessment of patient engagement and the presence of shared decision making between counseling provided before and after implementation of the decision support tool by providers randomized to the intervention group. As described above, the qualitative coding will focus on the presence or absence of shared patient-provider decision making and patient engagement in the decision making process, drawing on concepts from observational measures of shared decision making, as well as insights into the counseling process gained through our previous observational study.

Specific Aim 3:

- Qualitative assessment of providers' and staff members' experiences using interviews and focus groups
- Quantitative measures of consultation time and total clinic visit time
 - Total Clinic Visit Time
 - Total amount of time a patient spends in a clinic for a family planning visit, from check-in to check-out.
 - Time Spent with Contraceptive Counseling Provider
 - Total amount of time spent with the provider that is providing contraceptive counseling.
- Change in provider burnout, pre- and post-intervention, using the Maslach Burnout scale, measured prior to implementation of the intervention and at the end of the trial
 - Maslach Burnout Inventory:
 - Given to provider participants to measure emotional exhaustion, depersonalization, and personal accomplishment subscale scores.

Timing of Measures

Patient Outcomes

	Baseline clinic visit	4 months	7 months
Demographics	X		
Chosen method	X		

Study Protocol

Patient Centered Support for Contraceptive Decision-Making: A Cluster Randomized Controlled Trial of a Contraceptive Decision-Support Tool

November 22, 2016

Continuation of chosen method		X	X
Use of non-barrier method		X	X
Decisional conflict	X		
Attitudes Knowledge of contraceptive options	X		
Satisfaction with contraceptive counseling	X	X	X
Incidence of unplanned pregnancy		X	X
Total clinic visit time	X		
Time spent with contraceptive counseling provider	X		
Satisfaction with chosen method	X	X	X
Satisfaction with current method		X	X

Provider Outcomes

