 - For the 5-point Likert scale question regarding satisfaction with support provided/how the provider helped you to choose, we will do top scoring
 - For the question regarding satisfaction with involvement of provider in the decision making process, we will analyze using the existing three categories (no collapsing)
 - For the question regarding satisfaction with the degree to which provider expressed preference, responses will be collapsed into 3 categories:
 - 1) A lot less strongly AND less strongly
 - 2) Exactly right
 - 3) A little bit more strongly AND a lot more strongly
- Patient Decisional Conflict in Contraceptive Choice at the post-visit survey

- Validated survey to assess patients' decisional conflict in medical decision making.
 - In primary analysis, we analyze this scale as a continuous variable. We will dichotomize if this violates linearity assumptions.
- Patient Current Contraceptive Method Satisfaction at 4 and 7 months
 - 5-point Likert scale question regarding patient satisfaction with the contraceptive method they are currently using.
 - In primary analysis we will do top-scoring, i.e. a score of 5 versus all other scores
- Patient Attitudes and Knowledge of Contraceptive Options and Features (post-visit survey)
 - Patient report of perceived knowledge of their options and questions derived from National Survey of Reproductive Contraceptive Knowledge and previous studies of contraceptive knowledge and attitudes.
 - In primary analysis:
 - Will analyze each of these questions independently. For the questions related to effectiveness and the questions related to knowledge of IUDs, we will also analyze as either answering all questions correctly vs. answering any incorrectly, and also examine the number correct as an ordinal outcome.
 - For all knowledge and attitudes question, unless otherwise specified below, we will analyze answered correctly vs. incorrectly or I don't know
 - Emergency contraceptive knowledge question:
 - 1) Primary analysis: selection of emergency contraception AND copper IUD vs. not selecting both of those
 - 2) Sensitivity analysis: for having copper IUD in their answer vs. not
 - For the "Heard of" question: we are pre-specifying interest in responses regarding IUDs (analyzed together), implant, vasectomy, female sterilization, patch, and ring, with a primary interest in IUDs
 - 1) IUD primary analysis: heard of an IUD (either one) vs. not having heard of it
 - 2) Equivalent analyses for other methods

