We will assess imbalance by treatment assignment using cross-tabulations and comparisons of within group means and medians. Inference for balance on provider covariates will use chi-squared, Fisher's exact, t, and Wilcoxon tests as appropriate, while differences in patient characteristics will be assessed using mixed effects models with fixed effects for clinic and random effects for provider. [IR-3] Primary analyses of treatment effects will be intention-to-treat, according to treatment assignment, and without regard to use of the tool or seeing an intervention provider. Treatment effects will be estimated using mixed effects linear, logistic, proportional odds, and multinomial models, with fixed effects for clinic and random effects for provider.

Missing data. [MD-1] Missing data will have been minimized by active follow-up of participants. [MD-4] Missing data rates for primary and secondary outcomes as well as important covariates will be reported, in combination with summaries of the reasons for missingness, including dropout and pregnancy. [MD-2] All analyses will handle missing data using 20-fold multiple imputation of missing outcomes, based on iterative chained equations. [MD-3] Summary effect estimates, averaged over the 20 imputed datasets, as well as confidence intervals and p-values, will be calculated using standard methods that account for imputation error.

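### The pre-visit survey of knowledge and preferences has no role in the main models for the post-visit knowledge, attitude and method-choice outcomes

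*Protocol*

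**What the plan says.** Protocol III.B (patient procedures): after consent, "each patient will complete a pre-visit survey regarding their contraceptive knowledge and preferences". The step is not restricted by arm. Where appointments are made with a named provider, "arm assignment will be recorded upon completion of the pre-visit survey". A later step says that in the intervention arm "she will interact with the MyBirthControl contraceptive decision support tool while in the waiting room". So the survey precedes exposure to the tool.

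SAP, Secondary outcomes, lists "Patient Attitudes and Knowledge of Contraceptive Options and Features (post-visit survey". Unless otherwise specified, the rule for these items is that "we will analyze answered correctly vs. incorrectly" or don't-know answers. Ratings of individual methods are continuous on an 11-point scale, and choice of a highly effective method is Tier 1 against everything else. None of these definitions mentions a pre-visit value or a change score.

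SAP, Methods of Analysis, Specific Aim 1: "Treatment effects will be estimated using mixed effects linear, logistic, proportional odds, and multinomial models, with fixed effects for clinic and random effects for provider". The pre-specified patient covariates are age, parity, race/ethnicity, language and parental education.

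The Protocol's Timing of Measures table shows "Attitudes Knowledge of contraceptive options" under a single baseline-visit column and does not display the pre-visit survey.

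For provider burnout, Protocol VII.B (Specific Aim 3) adjusts the final score for its baseline value and gives power as the reason.

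**The concern.** What a woman knew or preferred shortly before the visit is a natural predictor of what she reports just after it. If it is left out of the model, the variation it explains stays in the error term and the intervals are wider than they need be.

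The design adds a second reason. Only 24 providers are randomised, and patients are recruited afterwards. A patient's arm often follows the appointment schedule or, at the two clinics without named appointments, which provider is free or speaks her language. Arms may therefore differ in prior knowledge or preference, and a post-visit-only comparison carries any such difference into the estimate.

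The plan accepts baseline adjustment for burnout. It gives no reason for not using the patients' own pre-visit survey in the same way.

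**Working it through.** **1. The plan's own figure.** The only planning figure for an outcome at issue here is the method-choice row in Protocol VII.B: baseline 23%, design effect 0.9, minimum detectable difference (MDD) 10.9 points. I used the pooled two-proportion formula, n per arm = DE × [1.960√(2p̄q̄) + 0.842√(p₁q₁ + p₂q₂)]² / (p₂ − p₁)².

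- With 758 × 0.8 ≈ 606 evaluable, the MDD is 9.7 points.
- With 606 / 1.12 ≈ 541, it is 10.3 points.

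Neither gives 10.9. The 1.12 is close to the factor left over in the main calculation: 50% v 62% needs 268 per arm, 536 in total and 536 / 0.8 = 670 after loss, and 758 / 670 = 1.13. The Protocol mentions an inflation factor without giving its size, so neither 758 nor 10.9 can be called wrong. I take 10.9 as given.

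**2. What adjustment could gain.** Let r be the correlation between the pre-visit value and the outcome. The documents give none, so every r below is an assumption. On a linear scale the residual variance is multiplied by 1 − r², and interval width and MDD by √(1 − r²). Power at the effect now detectable with 80% power becomes Φ[2.802/√(1 − r²) − 1.960].

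| r (assumed) | 1 − r² | CI narrowing | 10.9-point MDD becomes | Power from 80% to |
|---|---|---|---|---|
| 0.2 | 0.96 | 2.0% | 10.7 | 81.6% |
| 0.3 | 0.91 | 4.6% | 10.4 | 83.6% |
| 0.5 | 0.75 | 13.4% | 9.4 | 89.9% |
| 0.7 | 0.51 | 28.6% | 7.8 | 97.5% |

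The approximation suits the continuous method ratings best. For binary outcomes it is only a rough guide on the risk-difference scale, and it takes no separate account of clustering.

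**3. How large chance imbalance might be.** The standardised difference between arms in a pre-visit score has SD √(4 × DE / N). I borrow the design effects 0.9 to 1.7 from the Protocol's secondary-outcome table; none is given for a pre-visit score.

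| N | SD of imbalance | P(above 0.1 SD) | P(above 0.2 SD) |
|---|---|---|---|
| 758 (all enrolled) | 0.07–0.09 | 15%–29% | 0.4%–3% |
| 606 (after 20% loss) | 0.08–0.11 | 19%–35% | 1%–6% |

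At r = 0.5, an imbalance at the 95% limit shifts an unadjusted estimate by 0.5 × 1.96 × SD: about 0.07–0.09 SD with 758, or 0.08–0.10 SD with 606.

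**4. Whether the planned sensitivity analysis recovers this.** It covers patient characteristics that are imbalanced and predict the outcome, and keeps those that move the treatment coefficient by 5%. In a linear model, adding a covariate moves that coefficient by (covariate slope) × (imbalance). With no imbalance the shift is zero however strong the slope, so the covariate stays out. The rule selects on imbalance, whereas the precision gain in step 2 depends on prognostic strength alone.

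**The case against.** **Item overlap is not documented.** Neither questionnaire is in the documents, and the pre-visit survey is described only by topic. A reader might infer that every post-visit knowledge item, method rating and method choice has its own same-item baseline; the text does not show this. The point stands, and it makes the fix conditional.

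**The plan already has a safeguard.** A reader might infer that protection against imbalance is abandoned altogether. It is not: balance checks are planned, randomisation is stratified by clinic, clinic is a fixed effect, and the sensitivity analysis gives its covariates only as examples, so a pre-visit score could qualify. It might qualify often. With an illustrative effect of 0.25 SD (the Protocol's figure for decisional conflict) and a standardised slope of 0.5, an imbalance of 0.05 × 0.25 / 0.5 = 0.025 SD meets the 5% rule. But the separate condition that a characteristic be imbalanced is not defined, the survey is not named, and the main estimate stays unadjusted in any case.

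**The gains do not carry over to logistic models.** Correct. In the planned logistic mixed models, a prognostic covariate changes the conditional odds ratio and need not narrow its interval, although power can still rise. Most of these outcomes are binary, so the table in the working should not be read as a forecast for them.

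**The burnout comparison is imperfect.** There the same instrument is documented at both times, and the sample is 24 providers with admittedly limited power. It shows that the plan accepts the principle, not that the gain would be similar.

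**Imputation.** A reader might infer that pre-visit answers are excluded from the imputation. The predictors are simply not listed.

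**The timing table.** The single column is a matter of presentation: the outcome lists say post-visit plainly.

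**Conclusion.** The omission is clear from the text: a measure of the same broad constructs, taken before the tool is used, has no assigned role in the main analysis of these outcomes. The unadjusted intention-to-treat comparison is not invalidated by this. What is lost is precision, together with firm, pre-specified protection against imbalance.

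The size is uncertain. It depends on item overlap and on r, and runs from negligible (about 2% narrower intervals at r = 0.2) to material (13% at 0.5, 29% at 0.7), on a linear approximation that fits the continuous ratings best. For method choice it also depends on whether a pre-visit method preference was recorded, which the documents do not say.

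Only secondary outcomes are involved. It would be tempting to treat this as a weakness of the trial's main result, but the analysis of seven-month continuation and the 758-patient calculation do not rest on it. Confidence is high on the omission and moderate at best on the gain.

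**What to change.** 1. List in the SAP which pre-visit items match which post-visit outcomes, working from the questionnaires and not from the data.
2. For each knowledge or attitude outcome with a matching item, enter the pre-visit answer as a fixed covariate in the main model. Where no item matches, use a pre-visit knowledge score.
3. For choice of a highly effective method, enter pre-visit method preference, if it was collected.
4. For binary outcomes, report a standardised risk difference, so that the estimate stays marginal, with an interval that respects provider clustering.
5. Name the pre-visit answers among the predictors in the chained-equation imputation. This also helps with the items not asked of women surveyed after 48 hours.
6. Keep the present model (arm, clinic, provider) as a supplementary analysis.
7. Split the baseline column of the timing table into pre-visit and post-visit surveys, for clarity.

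The cost is SAP wording and a few model terms. The Protocol's data-management section says patient surveys are administered in REDCap, so no new data collection is needed for whatever the survey contains. The change should be dated and made before any comparison by arm.
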